### **2.2      Secondary Objective(s)**

To evaluate the following:

1. The safety profile of the combination of azacitidine and ascorbic acid in the targeted patient population.
2. The response duration for study patients.
3. The overall survival of the treated population (compared to matched historical cohort of patients treated with single agent Azacitidine)
4. The identification of genomic biomarkers that may predict response to the combination treatment.

5. Evaluation of changes in methylation prior and during therapy

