#### **4.1 Subject Selection**

#### **4.2 Inclusion Criteria**

Subjects must meet all of the following inclusion criteria to be eligible for enrollment:

4.2.1 Patients must have a confirmed *TET2* mutations identified by next generation targeted deep sequencing.

4.2.2 Patients must have MDS, or MDS/MPN overlap defined by 2016 WHO criteria. Both newly diagnosed or previously treated MDS or MDS/MPN patients are eligible as long as the patient has never received prior treatment with azacitidine or decitabine.

4.2.3 Patients with Leukemic/blast phase transformation MPN.

4.2.4 Patient with AML according to 2016 WHO criteria (excluding APL [AML-M3]).

4.2.4.1 Newly diagnosed patients who are ineligible or declined to receive intensive chemotherapy after discussion of risks and benefits of that approach or patients with primary refractory/relapsed AML.

4.2.4.2 Patients with active central nervous system (CNS) leukemia eligible at the discretion of treating physician.

4.2.4.3 Relapse/Refractory is defined as at least 1 course of treatment for AML excluding any patients treated with azacitidine or decitabine.

4.2.4.3.1 Patients should be off any prior treatment or line of therapy for 2 weeks prior to start study with the exception of hydrea (Hydroxyurea).

4.2.5 Prior therapy with hydroxyurea, biological or targeted therapy (e.g. flt3 inhibitors, other kinase inhibitors) or hematopoietic growth factors is allowed.

4.2.6 Age  $\geq 18$  years.

4.2.7 ECOG performance status  $\leq 3$ .

4.2.8 Patients must have normal organ and marrow function as defined at the discretion of the treating physician and PI.

- 4.2.9 Women of childbearing potential must have a negative serum or urine pregnancy test within 10-14 days prior to enrollment.
- 4.2.10 Patients must have the ability to understand and the willingness to sign a written informed consent document.
- 4.2.11 Patient must be willing to comply with all aspects of the protocol including completing the drug diary.
- 4.2.12 Patient must discontinue any and all use of multivitamin and/or vitamin c medication 24 hours before first dose of Ascorbic Acid.

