###### **6.1.1 Azacitidine**

Azacitidine will be administered intravenously or subcutaneously at a fixed dose of 75mg/m^2/day for 7 consecutive days, allowing interruptions for weekends and holidays within each 28-day cycle. No dose modifications will be permitted during the treatment period.

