#### **6.1.2 Ascorbic Acid**

Ascorbic acid will be administered orally daily at 1 g/day three days prior to start azacitidine and then continues daily for a total of 28 days of each 28 day cycle. No dose modifications will be permitted during the treatment period.

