**Definition of secondary outcomes/endpoints:**

1. Incidence of adverse events of the combination defined by CTCAE 4.1 criteria.  
Toxicity will be any drug related Grade 3 or 4 toxicity.
2. Response duration to the combination recorded from start of treatment to progression
3. Overall survival measured from start of treatment to death or last follow up

**Sample size justification and study design:** The study sample size was determined using Minimax Simon's two-stage design (Simon, 1989. The null hypothesis that the true response rate is 0.3 will be tested against a one-sided alternative that the true response rate is 0.5. In the first stage, 12 patients will be accrued. If there are 3 or fewer responses, the study will be stopped. Otherwise, 16 additional patients will be accrued for a total of 28. The null hypothesis will be

rejected if 11 or more responses are observed in 28 patients. This design yields a type I error rate of 0.1 and a power of 0.8 when the true response rate is 0.5.

**Analysis plan:** Descriptive statistics will be used for the primary endpoint and secondary endpoints 1,2, and 3. Overall survival will be estimated with Kaplan Meier method and will be compared to the survival of a historical cohort of MDS patients treated at our institution with single agent Azacitidine between 2006-2012 using a one-sample log rank test. A Cochran-Mantel-Haenszel test will be used to test for differences in response rate by mutational status controlling for treatment. Unadjusted and adjusted logistic regression models were used to predict response to therapy. Models will be adjusted for covariates including age, sex, and other prognostic factors. The odds ratio (OR) and 95% confidence intervals (CI) will be estimated for the risk group (mutated) and compared with the reference group (WT).

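### The biomarker CMH test controls for treatment, but there is only one treatment, so nothing is adjusted; disease type, which sets the response definition, is not a stratum

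*Combined protocol and SAP*

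**What the plan says.** The analysis plan in Section 14.0 states: "A Cochran-Mantel-Haenszel test will be used to test for differences in response rate by mutational status controlling for treatment". No other stratification factor is given for this test. Logistic models for response follow, unadjusted and adjusted. For the adjusted ones, "Models will be adjusted for covariates including age, sex, and other prognostic factors". The odds ratio and its 95% confidence interval "will be estimated for the risk group (mutated) and compared with the reference group (WT"). These analyses serve secondary objective 4 in Section 2.2: "The identification of genomic biomarkers that may predict response to the combination treatment".

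Five other parts of the protocol bear on this:

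- **Treatment.** Sections 3.0, 6.1.1 and 6.1.2 describe one regimen for everyone: "Azacitidine will be administered intravenously or subcutaneously at a fixed dose", and "Ascorbic acid will be administered orally daily at 1 g/day three days prior to start azacitidine and then continues daily". Section 7.0 allows no dose modification. No second arm is described.
- **Historical cohort.** The only other treatment group in the plan appears in the survival comparison. Overall survival "will be compared to the survival of a historical cohort of MDS patients treated at our institution with single agent Azacitidine". Section 2.2 gives the cohort the same single use.
- **Entry.** Item 4.2.1 requires confirmed TET2 "mutations identified by next generation targeted deep sequencing". Item 4.2.3 also admits blast-phase MPN.
- **Panel.** Section 10.0 plans a 170-gene panel before treatment.
- **Response.** Section 14.0 counts CR, PR or HI (IWG 2006) for MDS and MDS/MPN, and CR, CRp, CRi or PR (IWG 2003) for AML. Blast-phase MPN is not assigned to either set.

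**The concern.** A Cochran-Mantel-Haenszel test adjusts by comparing within strata. If the stratifying variable takes one value in every patient, nothing is adjusted. A reader told that a biomarker result controlled for treatment would credit it with a safeguard it does not have.

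The variable that does vary, and that helps determine the outcome, is disease type. HI makes a patient a responder in MDS or MDS/MPN but not in AML; CRp and CRi do so only in AML. Suppose response rates differ by disease and a gene is also more frequent in one disease. That gene will then be associated with response in the pooled table even if it has no effect within either disease. The test as written does not remove this confounding.

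The comparison is also not identified. With a TET2 mutation required for entry, no trial patient is TET2 wild-type, so a mutated versus wild-type contrast can only concern other genes on the panel. The plan does not say so. A programmer would have to guess both the stratum and the gene.

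What is at stake is the credibility of a secondary biomarker finding. The primary test of response is not affected by this sentence.

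**Working it through.** **Inputs from the protocol.** N = 28 (Section 3.1); one treatment level (Sections 3.0, 6.1.1, 6.1.2, 7.0); two response definitions by disease (Section 14.0). The plan gives no alpha, power, effect size or gene list for this test, so it has no figure to reproduce.

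**Step 1: what the test reduces to.** For a 2×2 table with cells a, b, c, d and total N, the one-stratum CMH statistic without continuity correction is

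[a − (a+b)(a+c)/N]² ÷ [(a+b)(c+d)(a+c)(b+d) / (N²(N−1))] = Pearson chi-square × (N−1)/N.

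At N = 28 the factor is 27/28 = 0.964, and the Mantel-Haenszel odds ratio equals the crude odds ratio. For cells 8, 4, 5, 11: Pearson 3.458 × 27/28 = 3.335, the CMH value, and the odds ratio is 4.40 either way. The test is valid but unadjusted.

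**Step 2: how disease can mislead it (assumed table).** Take 16 MDS or MDS/MPN and 12 AML patients, and a gene with no effect within disease.

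| | Mutated, responders | Wild-type, responders |
|---|---|---|
| MDS or MDS/MPN | 9/12 (75%) | 3/4 (75%) |
| AML | 1/4 (25%) | 2/8 (25%) |
| Pooled | 10/16 | 5/12 |

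Pooled odds ratio = (10 × 7)/(6 × 5) = 2.33 (chi-square 1.15, p = 0.28). Stratified by disease, the odds ratio is 1.00 and the chi-square 0.

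**Step 3: false-positive rate per gene.** All mutation and response counts in each disease were enumerated, rejecting when the CMH chi-square exceeds 3.8415 (nominal two-sided 0.05). The gene has no effect within disease. The scenarios are assumptions, given as MDS or MDS/MPN versus AML:

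- A: response 40% vs 40%, gene 20% vs 50%
- B: response 50% vs 30%, gene 20% vs 40%
- C: response 50% vs 30%, gene 10% vs 50%
- D: response 50% vs 20%, gene 10% vs 50%
- E: response 60% vs 20%, gene 10% vs 60%

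Each cell shows as written / stratified by disease, in %. The mix is MDS or MDS/MPN + AML.

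| Mix | A | B | C | D | E |
|---|---|---|---|---|---|
| 14+14 | 5.0 / 4.9 | 5.2 / 4.7 | 6.8 / 4.7 | 9.2 / 4.1 | 19.5 / 4.0 |
| 20+8 | 4.9 / 4.8 | 5.1 / 4.7 | 6.0 / 4.3 | 7.6 / 3.7 | 16.6 / 3.8 |
| 8+20 | 4.8 / 4.9 | 5.0 / 4.8 | 6.0 / 4.8 | 7.6 / 4.4 | 14.6 / 4.2 |
| 24+4 | 4.7 / 4.4 | 4.9 / 4.5 | 4.5 / 3.3 | 5.0 / 3.1 | 9.8 / 3.2 |

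Crude odds ratio in E at 14+14, from expected counts: mutated responders 1.4 × 0.6 + 8.4 × 0.2 = 2.52 of 9.8; wild-type responders 12.6 × 0.6 + 5.6 × 0.2 = 8.68 of 18.2. The ratio is (2.52 × 9.52)/(7.28 × 8.68) = 0.38, when the true value is 1. For 20+8, 8+20 and 24+4 it is 0.40, 0.46 and 0.50.

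**Step 4: power given up by stratifying.** Assume the gene is present in 30% of each disease and wild-type response is 30%.

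| Odds ratio | As written | Stratified (14+14, 20+8, 24+4) |
|---|---|---|
| 8 | 65.5% | 62.9%, 62.9%, 62.7% |
| 5 | 47.1% | 44.7%, 44.6%, 44.4% |

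**Step 5: room in the logistic model.** At the design response rates of 30% to 50%, responders number 0.3 × 28 = 8.4 to 0.5 × 28 = 14. With mutation, age and sex (3 terms) there are 8.4/3 = 2.8 to 14/3 = 4.7 responders per term. Adding disease type (4 terms) gives 8.4/4 = 2.1 to 14/4 = 3.5.

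**The case against.** The strongest reply is that the phrase about treatment is a harmless drafting slip. A one-stratum CMH is a valid test, and an unadjusted screen followed by adjusted models is ordinary practice in a 28-patient phase II trial. The adjusted logistic models follow in the same paragraph, with an open covariate list that could include disease type. The primary endpoint itself pools across diseases. The documents support none of the assumed scenarios, and material inflation appears only when both response and gene frequency differ strongly by disease. Multiplicity may well be the larger problem: if 10 independent genes were each tested at a true 5% (an assumption), the chance of at least one false positive would be 1 − 0.95¹⁰ = 40% with no confounding at all. Finally, the author may have meant to pool response with the historical cohort, which would give treatment two levels.

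Much of this stands, and it is why the point is minor. The gap is certain for the CMH test but only unspecified for the regression. Scenario E is a bound and should not drive the judgement. Stratifying does not address multiplicity.

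The pooling reading has no support in the text: the historical cohort is assigned to survival only and is described as MDS only. Nor does the reply remove the core problem. The plan states an adjustment that cannot happen, and leaves out the factor on which its outcome definition depends.

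**Conclusion.** The concern holds and is minor. From the text alone it is certain that controlling for treatment does nothing here, that disease type is not a CMH stratum, and that TET2 cannot be the gene compared.

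The size of the harm is not known. Under the assumptions above, the excess over the nominal 5% is at most 1.8 points in scenarios A to C. It is at most 4.2 points in D, and 4.8 to 14.5 points in E. There is essentially no excess when response does not differ by disease (scenario A), and with only four AML patients there is none in A to D. Real harm needs large differences in both response and gene frequency, and neither disease group very small.

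The analysis is secondary, carries no alpha and drives no go/no-go decision. The missing response criteria for blast-phase MPN matter here only because a disease stratum cannot be built without them; they add no weight to this point.

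**What to change.** In the Section 14.0 analysis plan:

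1. Replace the CMH sentence with: *For each panel gene other than TET2, response will be compared between mutated and wild-type patients by a Cochran-Mantel-Haenszel test stratified by disease type (MDS or MDS/MPN versus AML).*
2. Name disease type as a covariate in the adjusted logistic model, beside age and sex.
3. Label the analysis exploratory and report how many genes were tested.
4. State which response criteria and which stratum apply to blast-phase MPN.
5. If a pooled response analysis with the historical cohort was intended, say so and describe it.

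An exact or mid-p version of the test is optional.

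The cost is wording and minor programming; disease type and panel results are already collected. There are three statistical costs. Power falls by about 2 to 3 points under the assumptions in step 4. The stratified test becomes conservative if one disease group is very small (3.1–4.5% at 24+4). If disease type was not already among the unnamed prognostic factors, it also adds one term to a thin logistic model, taking responders per term from 2.8–4.7 to 2.1–3.5.

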**APPENDIX I**  
**PERFORMANCE STATUS CRITERIA**

ECOG Performance Status Scale		Karnofsky Performance Scale	
Grade	Description	Percent	Description
0	Normal activity. Full active, able to carry on all pre-disease performance without restriction.	100	Normal, no complaints, no evidence of disease.
		90	Able to carry on normal activity; minor signs or symptoms of disease.
1	Symptoms, but ambulatory. Restricted in physically strenuous activity, but ambulatory and able to carry out work of a light or sedentary nature (e.g., light housework, office work).	80	Normal activity with effort; some signs or symptoms of disease.
		70	Cares for self, unable to carry on normal activity or to do active work.
2	In bed < 50% of the time. Ambulatory and capable of all self-care, but unable to carry out any work activities. Up and about more than 50% of waking hours.	60	Requires occasional assistance, but is able to care for most of his/her needs.
		50	Requires considerable assistance and frequent medical care.
3	In bed > 50% of the time. Capable of only limited self-care, confined to bed or chair more than 50% of waking hours.	40	Disabled, requires special care and assistance.
		30	Severely disabled, hospitalization indicated. Death not imminent.
4	100% bedridden. Completely disabled. Cannot carry on any self-care. Totally confined to bed or chair.	20	Very sick, hospitalization indicated. Death not imminent.
		10	Moribund, fatal processes progressing rapidly.
5	Dead.	0	Dead

## APPENDIX II

### CYCLE 1 SUBJECT PILL DIARY

Subject Name \_\_\_\_\_ Protocol # \_\_\_\_\_ Subject Study ID \_\_\_\_\_  
Cycle #: \_\_\_\_\_ Month #: \_\_\_\_\_

#### INSTRUCTIONS FOR THE SUBJECT:

1. You will take 1 tablet of 1000 mg of Ascorbic Acid (Vitamin C) pills each day. *Take the tablets with food*
2. Record the date, the number of tablets you took, and what time you took them.
3. If you have any comments please record them in the "Comments" column below.
4. Please bring your pill bottle and this form to your physician when you come for your next appointment.
5. Please sign your name at the bottom of the diary.

Date	Day	Time	# of 1000 mg Ascorbic Acid (Vitamin C) pills and time taken	Comments
	-3			
	-2			
	-1			
	1			
	2			
	3			
	4			
	5			
	6			
	7			
	8			
	9			
	10			
	11			
	12			
	13			
	14			
	15			
	16			
	17			
	18			
	19			
	20			
	21			
	22			
	23			
	24			
	25			
	26			
	27			
	28			

Subject's Signature:

Date:

### APPENDIX III

#### CYCLE 2 + SUBJECT PILL DIARY

Subject Name \_\_\_\_\_ Protocol # \_\_\_\_\_ Subject Study ID \_\_\_\_\_  
Cycle #: \_\_\_\_\_ Month #: \_\_\_\_\_

**INSTRUCTIONS FOR THE SUBJECT:**

1. You will take 1 tablet of 1000 mg of Ascorbic Acid (Vitamin C) pills each day. *Take the tablets with food*
2. Record the date, the number of tablets you took, and what time you took them.
3. If you have any comments please record them in the "Comments" column below.
4. Please bring your pill bottle and this form to your physician when you come for your next appointment.
5. Please sign your name at the bottom of the diary.

Date	Day	Time	# of 1000 mg Ascorbic Acid (Vitamin C) pills and time taken	Comments
	1			
	2			
	3			
	4			
	5			
	6			
	7			
	8			
	9			
	10			
	11			
	12			
	13			
	14			
	15			
	16			
	17			
	18			
	19			
	20			
	21			
	22			
	23			
	24			
	25			
	26			
	27			
	28			
Subject's Signature: _____				Date: _____

#### **APPENDIX IV: STUDY DESIGN TIME POINT DEFINITIONS**

Study Time Points	Definitions
Screening	Screening will occur from the time of the consent until day -4
Baseline/Enrollment	Days -17 b to Day -3 c
Treatment Period	Day 1 c to C6D28 or patient meets end of treatment criteria before completing 6 cycles
Extended Treatment Period (ETP)	The extended treatment period is defined as C7D1 to the patient meets EOT criteria
Study Treatment	The treatment period and if applicable the extended treatment period
End of Treatment (EOT)	The day patient meets the defined EOT criteria (Table 1) and discontinues study treatment.
Follow up	Patient will be followed bimonthly (60 days +/- 7 days) for a duration of 1 year after study
End of Study (EOS)	The time the patient completes 1 year of survival follow up and/or patient's death, whichever were to occur first.

A: Day 1 is defined as first dose of Azacitidine  
B: Day -17 is defined as 14 days prior to first dose of study Drug (Day -3)  
C: Day -3 is defined as day of Study Drug

#### **APPENDIX V: RESPONSE CRITERIA FOR EXTENDED TREATMENT**

Response Criteria for extended treatment eligibility

- complete remission, partial remission, or hematologic improvement (CR/PR/HI) per IWG 2006 criteria for patients with MDS
- (CR/PR/marrow CR) per IWG 2003 criteria for patients with AML
- If the response is stable disease and the investigator determines the patient is gaining clinical benefit, patient may continue on treatment until progression.

## **APPENDIX VI: CLINICAL LABORATORY PARAMETERS**

Hematology	Serum Chemistry	Vitals	Physical Exam	Bone Marrow Biopsy & Aspiration
Red blood cell count	Sodium	Temp	Height(only at C1D1)	Marrow blast percent
Hemoglobin	Potassium	Pulse	Weight	Marrow Cellularity
Hematocrit	Chloride	Resp		Auer Rods
White blood cell count	Bicarbonate	Blood Pressure		Dysplasia
Neutrophil	BUN	SpO2*		Cytogenetics
Platelets	Glucose (non-fasting)			
Blasts percent	Albumin			
MCV	AST			
MCHC	ALT			
Eosinophils	Serum creatinine			
Basophils	Protein			
Monocytes	Calcium			
Lymphocyte	Bilirubin			
	Alkaline phosphate			

- This test should only occur at Screening visit

**APPENDIX VII: WHO classification of myeloid neoplasms and acute leukemia**  
**Arber et al, 2016**

**WHO myeloid neoplasm and acute leukemia classification**

**Myeloproliferative neoplasms (MPN)**

Chronic myeloid leukemia (CML), *BCR-ABL1*+

Chronic neutrophilic leukemia (CNL)

Polycythemia vera (PV)

Primary myelofibrosis (PMF)

PMF, prefibrotic/early stage

PMF, overt fibrotic stage

Essential thrombocythemia (ET)

Chronic eosinophilic leukemia, not otherwise specified (NOS)

MPN, unclassifiable

**Mastocytosis**

**Myeloid/lymphoid neoplasms with eosinophilia and rearrangement of *PDGFRA*, *PDGFRB*, or *FGFR1*, or with *PCM1-JAK2***

Myeloid/lymphoid neoplasms with *PDGFRA* rearrangement

Myeloid/lymphoid neoplasms with *PDGFRB* rearrangement

Myeloid/lymphoid neoplasms with *FGFR1* rearrangement

Provisional entity: Myeloid/lymphoid neoplasms with *PCM1-JAK2*

**Myelodysplastic/myeloproliferative neoplasms (MDS/MPN)**

Chronic myelomonocytic leukemia (CMML)

Atypical chronic myeloid leukemia (aCML), *BCR-ABL1*

Juvenile myelomonocytic leukemia (JMML)

MDS/MPN with ring sideroblasts and thrombocytosis (MDS/MPN-RS-T)

## **WHO myeloid neoplasm and acute leukemia classification**

MDS/MPN, unclassifiable

### **Myelodysplastic syndromes (MDS)**

MDS with single lineage dysplasia

MDS with ring sideroblasts (MDS-RS)

MDS-RS and single lineage dysplasia

MDS-RS and multilineage dysplasia

MDS with multilineage dysplasia

MDS with excess blasts

MDS with isolated del(5q)

MDS, unclassifiable

Provisional entity: Refractory cytopenia of childhood

### **Myeloid neoplasms with germ line predisposition**

### **Acute myeloid leukemia (AML) and related neoplasms**

AML with recurrent genetic abnormalities

AML with t(8;21)(q22;q22.1);RUNX1-RUNX1T1

AML with inv(16)(p13.1q22) or t(16;16)(p13.1;q22);CBFB-MYH11

APL with PML-RARA

AML with t(9;11)(p21.3;q23.3);MLLT3-KMT2A

AML with t(6;9)(p23;q34.1);DEK-NUP214

AML with inv(3)(q21.3q26.2) or t(3;3)(q21.3;q26.2); GATA2, MECOM

AML (megakaryoblastic) with t(1;22)(p13.3;q13.3);RBM15-MKL1

Provisional entity: AML with BCR-ABL1

AML with mutated NPM1

AML with biallelic mutations of CEBPA

## **WHO myeloid neoplasm and acute leukemia classification**

Provisional entity: AML with mutated RUNX1

AML with myelodysplasia-related changes

Therapy-related myeloid neoplasms

AML, NOS

AML with minimal differentiation

AML without maturation

AML with maturation

Acute myelomonocytic leukemia

Acute monoblastic/monocytic leukemia

Pure erythroid leukemia

Acute megakaryoblastic leukemia

Acute basophilic leukemia

Acute panmyelosis with myelofibrosis

Myeloid sarcoma

Myeloid proliferations related to Down syndrome

Transient abnormal myelopoiesis (TAM)

Myeloid leukemia associated with Down syndrome

**Blastic plasmacytoid dendritic cell neoplasm**

## **APPENDIX VIII: PROTOCOL AMENDMENT SUMMARIES**

Amendment Number/Version Number/Date: Amendment 1, protocol version 2, 11/20/2017	
Section #/page	Description of change (s)
Preparation for Intravenous Administration, pg 32	Corrected Chloride Injection or Lactated Ringer's Injection to Chloride Infusion or Lactated Ringer's Infusion.
Investigational Agents, pg 32	Added option to deliver Azacitidine to patients subcutaneously due to the national IV bag shortage.
Investigational Agents, pg 33	Corrected the dosages amount for the ascorbic acid as well as the amount of tablets.
Screen test procedures	Removed Vitamin C level testing
CLINICAL LABORATORY PARAMETERS, pg 53	Clarified that SpO2 testing should only occur at screening visit
Appendix IV, pg 54	Clarified days to align with study calendar
Study Calendar	Provided a 3 day window for each day 1 visit requiring a physician visit

Amendment Number/Version Number/Date: Amendment 2, protocol version 3, 05/24/2018	
Section #/page	Description of change (s)
Clinical Trials.gov number, pg 1	Added Clinical Trials.gov Number
Protocol Date and Protocol version number	Updated the protocol date and version number throughout the entire protocol.
Eligibility Criteria, pg 20	Updated the eligibility criteria from heterozygous TET2 mutations, to include all TET2 mutations
Background of Study Disease, pg 10-11	Updated rationale as to why the eligibility criteria is changing from heterozygous TET2 mutations, to include all TET2 mutations
Study Calendar, pg 43/44	Adding Cycle 1 Day 14 has a +/- 1 day window to account if the day falls on a holiday or weekend.
